1 Prevalence of HPV infection using self-sampling screening and
2 monitoring the Earlier Impact of HPV-Vaccination Program in
3 Switzerland
4
5

6 Study protocol – version 5

7 08 june 2016
8

- 9
10
11
- 12 • **Principal Investigator:** Pr [name], University Hospitals of Geneva,
13 Head of Gynecologic Division, [name], [contact]

14
15 ❖ **Co- investigators:**
16

17 [name], Msc, MPH, PhD cand. Institute of Global Health, Department of Health and
18 Community Medicine, University of Geneva and University of Applied Sciences Western
19 Switzerland, Geneva, Switzerland **Mail :** [contact]
20

21 [name], MD, Geneva Foundation for Medical Education and Research,
22 [contact]

23 [name] MD, University Hospitals of Geneva, Head of Gynecologic Division, CH-
24 [name], [contact].

25 [name], University Hospitals of Geneva, Head of Gynecologic Division, CH-
26 [name], [contact]

27 Pr [name], Institute of Global Health, Department of Health and
28 Community Medicine, University of Geneva, [contact]
29

30 **Abstract**

31

32 **Background:** Currently prevalence of HPV infections for high risk strains among young
33 women in Switzerland is unknown. In addition, since 2008 a vaccination program to prevent
34 these infections has been implemented in a number of cantons, but its actual population
35 impact is currently unknown. For now, HPV screening in Switzerland is mainly performed by
36 gynecologists or during gynecological consultation at hospital. This method is certainly
37 effective, but expensive; population coverage of screening is still insufficient. A whole
38 segment of the target population does not participate in this screening especially young
39 people of foreign origin, for various reasons: economic cost, no gynecological, and for other
40 reasons.

41 Several studies raise the effectiveness and efficiency of self-sampling to increase coverage
42 of screening, and the rate of participation of non-participants. Through this study, we
43 evaluate the possibility to use self-sampling as a screening tool in a real population,
44 document the effectiveness of this vaccination on the prevalence of HPV infections and
45 assess evolution of infection and clearance of HPV virus during 5 years in a population of
46 young unvaccinated and vaccinated girls.

47

48 **Method:** During the study, each woman will perform a vaginal swab sampling by auto to
49 research HPV. These samples will be sent to a laboratory where HPV typing is done by PCR
50 using the Anyplex™ II technology.
51 The study will focus on a sample of 400 young women. Participants must complete a
52 questionnaire containing demographic questions and their HPV immunization status.
53 Vaccination coverage expected in this population is about 50%. Depending on the state of
54 vaccination, two different groups will be vaccinated vs unvaccinated (200 women per group).
55 The cases of HPV infection are then calculated for each group and compared as a function
56 of the status of vaccination. Statistical tests will be applied McNemar's test for comparison
57 between the HPV prevalence rates between the 2 groups.

58

59 **Expected Results:** This study will allow us to confirm the possibility of using self-sampling
60 as a method of screening and monitoring of HPV infections in the general population, it will
61 also enable us to document the effectiveness of HPV vaccination by comparing prevalence
62 rate of HPV infections among a group of young girls vaccinated and not vaccine and assess
63 evolution of infection and clearance of HPV virus.

64 **Key words:** cervical cancer, self-sampling, Human papillomavirus (HPV)

65

66 1. Background

67 Human papillomavirus (HPV) vaccination to prevent cervical cancer has been introduced in
68 Switzerland in 2008. Recommendations are that young girls aged 11 to 14 are included in
69 the immunization schedule program at school and girls aged 15 to 19 are included in a
70 “catch-up program”, for a transition period, until 2012. Within school-based program, the
71 vaccine uptake has been achieved to date with a 60% course completion, but lower rate
72 (20%) has been observed in cantons having adopted an “opportunistic” vaccination strategy.
73 Monitoring public health impact is an essential component of the intervention. Since the
74 eventual cervical cancer disease reduction will be only able to be evaluated decades after
75 exposure, current monitoring activity will focus on the anticipated earlier reduction of HPV
76 vaccine-type in the population. In 2015, seven years passed since the first vaccinated
77 cohorts entered the program; “school-vaccinated” women will be of 18 years old and “catch-
78 up vaccination” will be of 32 years old. Prior introduction of the vaccine in Switzerland, the
79 only available data was from HPV testing performed with residual cervical screening sample
80 from women attending cervical cancer screening (1, 2). To date, there is no Swiss available
81 data about the impact of HPV vaccination. The earlier sign of HPV vaccination could
82 probably be observed on the HPV prevalence and precursor lesion in women population. To
83 date, there is no Swiss available data about the impact of HPV vaccination. The earlier sign
84 of HPV vaccination could probably be observed on the HPV prevalence and precursor lesion
85 in women population. An observational study conducted in Australia support that the
86 incidence of genital warts decreases in younger women (3-5). Another trial conducted in
87 England (6) has showed that the national HPV immunization program seemed successful in
88 preventing HPV 16/18 infection in sexually active young women. The prevalence of HPV
89 16/18 infection in the post-immunization survey was 6.5% amongst 16–18 year olds,
90 compared to 19.1% in the similar survey conducted prior to the introduction of HPV
91 immunization.

92 In USA, the US population-based sentinel surveillance system to monitor HPV impact show
93 that from 2008 to 2012, prevalence of HPV 16/18 in CIN2+ lesions statistically significantly
94 decreased from 53.6% to 28.4% among women who received at least one dose HPV vaccine
95 (*P*_{trend}<.001) but not among unvaccinated women (57.1% vs 52.5%; *P*_{trend}=.08) or women
96 with unknown vaccination status (55.0% vs 50.5%; *P*_{trend}=.71) (7). More recently, a
97 systematic review and meta-analysis describe that, in countries with female vaccination
98 coverage of at least 50%, HPV type 16 and 18 infections decreased significantly between the
99 pre-vaccination and post-vaccination periods by 68% (RR 0.32, 95% CI 0.19-0.52) and
100 anogenital warts decreased significantly by 61% (RR 0.39, 0.22-0.71) in girls 13-19 years of

101 age. Comparing to countries with female vaccination coverage lower than 50%, significant
102 reductions in HPV types 16 and 18 infection (RR 0.50, 95% CI 0.34-0.74]) and in anogenital
103 warts (0.86 [95% CI 0.79-0.94]) occurred in girls younger than 20 years of age, with no
104 indication of cross-protection or herd effects (8).

105 To evaluate the effectiveness of this vaccination, it is important to detect quickly,
106 economically and efficiently prevalence of HPV high risk in our population. In Switzerland,
107 young women who want to get tested do either with their gynecologists or so via
108 gynecological hospital visits. This method is certainly effective, but expensive, furthermore
109 screening coverage is still insufficient (only 30 to 40 % women's don't participate at the
110 screening) in Switzerland. Also a part of our study population don't participate in screening
111 such young people of foreign origin for various reasons, no gynecological medicine,
112 economic cost etc ...

113 Several studies raise the effectiveness and efficiency (9) of the self sampling to increase
114 screening coverage (10), participation rate of nonattenders (11, 12) self-sampling has been
115 nearly as sensitive as clinician-obtained cervical samples and more sensitive than cytology
116 for the detection of cervical intraepithelial neoplasia (CIN) for lesions of high-grade CIN-II or
117 higher (CIN-II+) (13-14) .

118 Through this study we want to evaluate the possibility of using self sampling as a screening
119 tool in a real population, yet a study in Geneva showed the possibility of its use for screening
120 a population not visiting gynecological hospital visits (15), but the actual population use
121 remains to be demonstrated.

122 **2. Objectives**

123 Through this study, we evaluate the possibility to use self sampling as a screening tool in a
124 real population, document the effectiveness of this vaccination on the prevalence of HPV
125 infections and assess evolution of infection and we will assess the evolution of viral
126 infection and clearance of throughout 5 years in a population of young, unvaccinated and
127 vaccinated girls.

128

129 **Primary objective**

- 130 • Explored the feasibility of establishing a home-based Self-HPV screening strategy in
131 general population

132

133 **Secondary objective**

- 134 • To determine the HPV prevalence of vaccine-type: 19 high-risk HPV types (16, 18, 26,
135 31, 33, 35, 39, 45, 51, 52, 53, 56, 58, 59, 66, 68, 69, 73, 82) and 9 low-risk HPV types(6,

136 11, 40, 42, 43, 44, 54, 61, 70) in young women population attending High schools in
137 Geneva and Faculty of Medicine at the University of Geneva.

138 • To generate data about vaccination impact and vaccine coverage.

139

140 • To assess the infection's evolution and clearance of HPV throughout 5 years in a
141 population of young, unvaccinated and vaccinated young women

142

143

144 **3. Material and method**

145

146 ***Inclusion criteria:***

147 • Eligible women aged between 18-31 years attending of Haute Ecole de Santé –
148 Genève and Faculty of Medicine at the University of Geneva.

149 • Understands study procedures and accepts voluntarily to participate by signing the
150 informed consent form (ICF)

151

152 ***Exclusion criteria:***

153 • History of hysterectomy or treatment on the cervix during the last 12 months.

154

155

156 **Study Design and Methods**

157

158 Setting: The study will be conducted in collaboration with the High school of health in Geneva
159 and Faculty of Medicine at the University of Geneva. The study will be proposed to 400
160 women attending these schools.

161

162 Recruitment: It will take place in the health school of health and Faculty of Medicine at the
163 University of Geneva. Trial information on the University website will be available; it will also
164 contain a phone number for helpline. Cards to check eligibility, registration and scheduling
165 will be available. The HPV self-collection kit will be directly distributed to participants at the
166 end of their courses to School of Health and University of Geneva School of Medicine

167

168 Data collection: Vaccination status, age, menopausal status, marital status, parity, tobacco
169 consumption, medical records, geographic data, consulting-date and HPV-test result.

170

171 HPV tests: The HPV self-collection kit included a dacron swab, collection tube, instructions
172 with explanatory pictures, consent forms and a participant demographic information. The

173 HPV analysis will be performed by Real-time PCR. Delay between sampling and lab
174 processing will be noted.

175

176 Technical aspect: Written informed consent will be obtained by papier. All women will
177 perform a self sampling for HPV testing using a simple swab with no medium. The results of
178 HPV testing and sociodemographic data will be archived in a database.

179

180 Statistical analysis: The expected vaccination coverage in this population is about 50%.
181 According vaccination status, 2 different groups will be formed (vaccinated vs non-
182 vaccinated). The cases of HPV infection (status HPV+) will then be calculated for each group
183 and compared according to the vaccination status. The applied statistical tests will be
184 McNemar's test for comparison.

185

186 Sample size: Sample size was obtained based on estimated prevalence of 6% of HPV 16/18
187 infection in the Swiss population aged less than 30 years. A total of 200 specimens per group
188 would be needed to detect about an 85% reduction in HPV 16/18 prevalence (prevalence of
189 0.9% in the vaccinated population), given an 80% power and a two-sided significance level of
190 95% (based on representative data from England). We therefore estimate that a sample size
191 of 400 women (200 in each group) will be adequate for the analyses.

192

193 Follow up: Participants will receive their results by e-mail directly via our colposcopy nurse.
194 We will follow the HPV-positive participants every 6 months during 5 years to assess the
195 evolution of their HPV status and the viral clearance. In order to do this, every 6 months they
196 will receive a self-sampling HPV kit at home, which they will return by mail to the
197 HUG for analysis.

198

199

200 **4. Statement regarding the relevance and potential contribution of the project to** 201 **cancer control**

202 Data from the registries will be used to assess the HPV prevalence of the pre-vaccine era
203 and will be the basis for monitoring infection after post-vaccine introduction. This study will
204 provide important data about the prevalence of HPV infection in a young and sexually active
205 population of women and on the proportion of vaccinated and non-vaccinated young women.

206 Despite the impact of vaccine on invasive cancers is not expected until some decades after
207 its extensive implementation, as the type-specific prevalence of HPV infection is very high in

208 young sexually active populations, the effect of a successful HPV vaccination program
209 should be quickly detected by sentinel surveillance in this sub-population.

210 Monitoring the impact of the vaccination programs by detecting type-specific infection is
211 important as it is the earliest anticipated change, and failure to detect protection from
212 infection will indicate failure to prevent cancer in the subsequent decades and allow the
213 implementation of appropriate changes in cervical cancer screening strategies.

214 This surveillance is required in order to document the expected gains in cancer prevention if
215 there is appropriate population coverage. In our case, no data is available in Switzerland.
216 Such surveillance would allow further studies to determine the duration of protection, long-
217 term safety and actual impact on health-care cost consumption.

218 In this project, 400 young girls will know their statuses for HPV infection and will obtain
219 information about this prevalent infection and offered sexual counselling. Those who test
220 positive for HPV infection will be guided to a gynaecological consultation for adequate
221 management.

222 By using self-sampling for HPV testing, we will demonstrate the potential benefit in terms of
223 participation, lower cost and feasibility to determine the prevalence of infection. This method
224 is much easier and cheaper than the current cervical cancer screening test used (Pap test),
225 which requires a gynaecological consultation. The self-sampling could be used to increase
226 the participation of young women in the cervical cancer screening programs and thereby
227 increase the effectiveness of the overall program screening.

228 In conclusion, monitoring HPV prevalence among sexually active young women in different
229 selected settings will provide an important early indication of HPV vaccine impact. These
230 data will also contribute to add important information for cervical cancer screening.

231

232 **5. Ethical issues**

233 The investigators commit that this study will be conducted in accordance with the Swiss law,
234 as well as in accordance with the recommendations of Good Clinical Practices (ICH E6-
235 1996) and the Declaration of Helsinki (Fortaleza, October 2013). Before the study starts, the
236 approval of the protocol by the Geneva Ethics Committee will be required, and all patients
237 will give their written informed consent to participate in the study.

238 All the participants will be informed of the HPV results and a webpage containing information
239 on the implications of having a positive result in women aged less than 30 years will be
240 available. Information can also be obtained via our colposcopy nurse (a helpline will be
241 available).

242

243 **6. Financial consideration**

244

245 This study includes no charge for the patients. Financial support was solicited for a 100%
246 research nurse for 12 months period (FRS 135'000), to buy kit sampling HPV (FRS 60) and
247 to Cepheid GeneXpert® System for HPV testing (equipment rental + Test cartridges) (FRS
248 40'000).

[figure not shown]
249

250 **7. References**

251 1. Petignat P, Faltin D, Goffin F, Billieux MH, Stucki D, Sporri S, et al. Age-related performance of
252 human papillomavirus testing used as an adjunct to cytology for cervical carcinoma screening in a
253 population with a low incidence of cervical carcinoma. *Cancer*. 2005;105(3):126-32.

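### McNemar's test, a test for paired data, is prescribed to compare two independent groups of women (vaccinated and unvaccinated)

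*Protocol*

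**What the plan says.** The test is named in two places in the protocol, both times for the comparison by vaccination status.

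- **Abstract, Method.** Infections are counted in each group and compared as a function "of the status of vaccination. Statistical tests will be applied McNemar's test for comparison" and, as the sentence goes on, "between the HPV prevalence rates between the 2 groups". The groups are described thus: "vaccination, two different groups will be vaccinated vs unvaccinated (200 women per group".
- **Section 3, Statistical analysis.** "According vaccination status, 2 different groups will be formed (vaccinated vs non"-vaccinated). HPV-positive cases are counted in each group "and compared according to the vaccination status. The applied statistical tests will be" "McNemar's test for comparison".

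No other inferential test appears in the document. Group sizes are expected, not fixed: "The expected vaccination coverage in this population is about 50" per cent.

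The Sample size paragraph of section 3 starts from two group prevalences ("Sample size was obtained based on estimated prevalence of 6% of HPV 16/18", against 0.9% in vaccinated women) and arrives at 200 women per group. It gives no rate of discordant pairs. The only repeated measurements are in the Follow up paragraph: HPV-positive women are resampled every 6 months for 5 years. McNemar's test is not assigned to those data.

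**The concern.** McNemar's test needs two linked binary observations per unit, such as the same woman on two occasions or the two members of a matched pair. It uses only the units on which the two observations disagree. Here every woman is either vaccinated or unvaccinated and has one baseline HPV result. An analyst told to run the test must therefore do one of two things.

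1. Feed in the 2x2 table of vaccination status by HPV status. The cells treated as discordant are then vaccinated HPV-negative and unvaccinated HPV-positive, and the null hypothesis becomes that vaccination coverage equals HPV prevalence. That is not the vaccine question.
2. Make up pairs of one vaccinated and one unvaccinated woman. The p-value then depends on who is paired with whom, and women in the larger group who have no partner are dropped.

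The conclusion about vaccine effectiveness is at stake. It is a secondary objective, since section 2 makes feasibility of home self-sampling the primary one, but it is the comparison on which the whole sample size was based.

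**Working it through.** **Inputs from the protocol (section 3, Statistical analysis and Sample size).** HPV 16/18 prevalence 6% unvaccinated and 0.9% vaccinated; 80% power; two-sided; 200 per group. The significance level is printed as 95% and is read here as alpha = 0.05.

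**Step 1: reproduce the stated sample size.** For two independent proportions with pooled variance and no continuity correction, the mean prevalence is p = (0.06 + 0.009)/2 = 0.0345 and

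n = [1.960 × √(2 × 0.0345 × 0.9655) + 0.842 × √(0.06 × 0.94 + 0.009 × 0.991)]² / (0.051)² = (0.506 + 0.215)² / 0.002601 = 199.85, so 200 per group.

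This is an exact match, so the stated figure is the one given by a calculation for unpaired groups. For comparison, the McNemar formula for unrelated pairs has discordant probabilities 0.06 × 0.991 = 0.0595 and 0.009 × 0.94 = 0.0085 (sum 0.0679):

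n = [1.960 × √0.0679 + 0.842 × √(0.0679 − 0.0026)]² / 0.002601 = 202.6, so 203 pairs.

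**Step 2: McNemar's test on the vaccination-by-HPV table, no vaccine effect.** With 6% positive in both groups of 200, the expected cells are:

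| | HPV+ | HPV− |
|---|---|---|
| Vaccinated | 12 | 188 |
| Unvaccinated | 12 | 188 |

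The cells compared are 188 (vaccinated, HPV−) and 12 (unvaccinated, HPV+):

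(188 − 12)² / (188 + 12) = 30,976 / 200 = 154.88, p about 1.5e-35 (exact binomial p about 8e-42).

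The difference 188 − 12 = 176 equals 200 vaccinated minus 24 infected, so the test compares coverage with prevalence. Exact enumeration gives a rejection rate above 99.99% when the vaccine does nothing. Simulation at an assumed prevalence of 30% in both groups also gives 100%.

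With a true effect, 12/200 against 2/200, the statistic is (198 − 12)²/210 = 164.7. It hardly differs from the null case. Fisher's exact test on the same data gives p = 0.011.

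**Step 3: McNemar's test on made-up pairs.** Averaged over random 1:1 pairings at 200 per group, type I error is 3.0% (exact version) or 5.3% (asymptotic), and power is 77% or 84%. For a single dataset the result still depends on the pairing. As an illustration with assumed counts of 60/200 and 43/200, let k be the number of pairs in which both women are positive. The statistic is (60 − 43)²/(103 − 2k) = 289/(103 − 2k):

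- k = 13: 289/77 = 3.75, just below the 3.84 cut-off, not significant;
- k = 14: 289/75 = 3.85, just above it, significant.

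About 41% of random pairings give p below 0.05. The independent chi-square test gives one answer, p = 0.052.

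Pairing also needs equal groups. With an assumed split of 160 to 240, 240 − 160 = 80 women would go unused.

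**Step 4: an independent-groups test at the planned size.** By exact enumeration at 200 per group:

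| Test | Power, 6% vs 0.9% | Type I error, 6% in both |
|---|---|---|
| Pearson chi-square | 85.1% | 4.7% |
| Fisher's exact | 76.5% | 3.0% |

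Fisher's exact test would need about 215 per group for 80% power.

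**The case against.** Nobody need run the test on the cross-table. The protocol says that prevalence is to be compared between the groups, and an analyst with that aim would notice that the cross-table version answers something else. If women are paired at random instead, the error rate is about nominal, so the result is ill-defined rather than wholly invalid. At the protocol's own planning values (about 12 against 2 positives) only three pairing outcomes are possible, with statistics 100/14, 100/12 and 100/10 and p-values 0.0075, 0.0039 and 0.0016. The conclusion is the same in all three. The sample size does not separate the two designs sharply either, because 203 pairs is close to 200. The vaccine comparison is also a secondary objective.

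Much of this stands as a limit on the supporting detail. The near-certain false positive belongs to the cross-table use only. The 60/43 example, the 30% prevalence and the 160/240 split are illustrations, not protocol figures. The sample size is an exact match to the unpaired formula, but it is weak evidence on its own.

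None of it rescues the stated test. The protocol defines no pairing and does not guarantee equal groups, and the literal application to the available table is badly wrong. Nor is this a detail left to a statistical analysis plan: a specific test is named twice, and a plan that named a suitable one would contradict the protocol.

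**Conclusion.** The concern holds. The only inferential test in the protocol is a paired test assigned to two unpaired groups. Used on the vaccination-by-HPV table, it rejects essentially always whether or not the vaccine works (154.9 on 1 degree of freedom with no effect, assuming 6% in both groups of 200). Used on invented pairs, it keeps roughly the right error rate on average, but its p-value is set by an arbitrary choice, and unmatched women are lost if the groups are unequal. Neither is acceptable as a prespecified analysis. This must be corrected before the vaccine comparison is made, even though that comparison is secondary, because the study was sized on it. The conclusion rests on the absence of any matching in the protocol and on one baseline HPV result per woman.

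**What to change.** In the Abstract (Method) and in section 3 (Statistical analysis), replace McNemar's test with a comparison of two independent proportions. Use Pearson chi-square without continuity correction, or Fisher's exact test if expected counts are small, and report the prevalence ratio or difference with a 95% confidence interval. State the rule for choosing between the tests in advance, because it affects power. At the planning values the expected number of positives is (12 + 1.8)/2 = 6.9 per group, so Pearson chi-square would normally apply and 200 per group is enough. With Fisher's exact test power falls to 76.5%.

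If McNemar's test is kept at all, confine it to change within the same woman between follow-up visits. It should not be used against baseline: only HPV-positive women are followed, so every followed woman is positive at baseline and can change in one direction only.

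The cost is one sentence in two places, with no new data and no change to the 400 women if Pearson chi-square is used.

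### The catch-up cohort's stated age of 32 contradicts the protocol's own dates; if the programme ages are right, the crude comparison by vaccination status mixes vaccination with birth cohort

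*Protocol*

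**What the plan says.** All places are in the protocol.

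- **Section 1, Background.** The programme starts in 2008: "Switzerland in 2008. Recommendations are that young girls aged 11 to 14 are included in" the school schedule. Girls of 15 to 19 are covered by a catch-up arm: "the immunization schedule program at school and girls aged 15 to 19 are included in a" catch-up programme, "for a transition period, until 2012". The same paragraph then moves seven years on, to 2015. It puts school-vaccinated women at 18 and says of the catch-up women: "up vaccination” will be of 32 years old".
- **Section 3, Inclusion criteria.** "Eligible women aged between 18-31 years attending of Haute Ecole de Santé" and the Faculty of Medicine. No reason is given for the limits 18 and 31.
- **Section 3, Statistical analysis.** "The expected vaccination coverage in this population is about 50" per cent. Two groups are formed by vaccination status, and their HPV-positive cases are compared with one test. Age has no stated part in this, although Data collection in the same section lists it as a recorded item.
- **Section 3, Sample size.** The planning prevalence of 6% refers to HPV 16/18 "infection in the Swiss population aged less than 30 years", which is a third age range. The planned effect is an 85% reduction, to 0.9%, with 200 women per group and 80% power.
- **Section 2, Objectives.** Feasibility of self-sampling is primary. Vaccination impact and coverage are secondary.

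**The concern.** The age of 32 does not follow from the start year and the catch-up ages given in the same paragraph. This reaches beyond the Background, because the eligible range runs well past the oldest age the programme could have reached on those dates. Women in the top part of the range would then have few or no vaccinated counterparts and would enter the comparison almost entirely on the unvaccinated side. If HPV prevalence differs between them and younger women, part of any difference between the groups reflects birth cohort and not vaccination.

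Section 4 of the protocol makes this worth settling. It treats infection prevalence as especially high in young sexually active women, and it would read a failure to see protection as a sign that cancer will not be prevented. The coverage estimate is also affected in its meaning: a proportion over all participants differs from a proportion over the cohorts that the programme targeted.

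**Working it through.** **1. Cohort ages.** Inputs from section 1: start 2008; school ages 11 to 14; catch-up ages 15 to 19, ending 2012; reference year 2015. The protocol is dated June 2016, so 2016 is shown as well.

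Age in reference year = age in programme year + (reference year − programme year).

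| Cohort | 2015 | 2016 |
|---|---|---|
| School, 11–14 in 2008 | 18–21 | 19–22 |
| Catch-up, 15–19 in 2008 | 22–26 | 23–27 |
| Catch-up, 15–19 in 2012 | 18–22 | 19–23 |

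The stated 18 reproduces (11 + 7). The stated 32 does not: the maximum is 19 + 7 = 26 in completed years, or 27 if the birthday falls late. Age 32 in 2015 needs 32 − 7 = 25 in 2008.

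**2. Who lies outside the programme, if 15 to 19 is right.** A woman aged 28 to 31 in 2016 was 20 to 23 in 2008. These are 4 of the 14 single-year ages from 18 to 31. The recruitment date is not stated; in 2017 the affected ages would be 29 to 31.

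**3. The plan's sample size.** Two-proportion normal approximation, pooled variance under the null, two-sided 5%, no continuity correction:

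Power = Φ[(|p1 − p2| − 1.96 × SE0) / SE1]

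With p1 = 0.06, p2 = 0.009 and 200 per group, SE0 = 0.01825 and SE1 = 0.01807. Power = Φ[(0.051 − 0.03577) / 0.01807] = Φ(0.84) = 80.0%. The 200 per group reproduces, and the age error does not enter it.

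**4. Illustration of the mixing.** These assumptions are not in the protocol: 10% of 400 participants (40 women) are 28 to 31; all 40 are unvaccinated, so they are 40/200 = 20% of that group; younger unvaccinated women have 6% prevalence; the older women have r times that.

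Unvaccinated prevalence = 0.80 × 6% + 0.20 × r × 6%.

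- r = 0.5: 4.8% + 0.6% = 5.4%
- r = 1.5: 4.8% + 1.8% = 6.6%

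If the vaccine had no effect, the vaccinated group would have 6%:

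- r = 0.5: 6/5.4 = 1.11, an apparent 11% increase
- r = 1.5: 6/6.6 = 0.91, an apparent 9% reduction

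With the planned effect (0.9% in the vaccinated), the true ratio of 0.15 would appear as 0.9/5.4 = 0.17 or 0.9/6.6 = 0.14. Power at r = 0.5 is Φ[(0.045 − 1.96 × 0.01747) / 0.01732] = Φ(0.62), about 73%. At r = 1.5 it is about 85%.

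**5. The extreme case, for scale.** If ages were uniform over 18 to 31, 4/14 × 400 = 114 women would be 28 to 31, or 57% of 200 unvaccinated. Unvaccinated prevalence is then 4.29% at r = 0.5 and 7.71% at r = 1.5, with power about 57% and 92%.

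**6. Cost of excluding the older women.** Power for 6% versus 0.9%, with 200 vaccinated:

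| Unvaccinated excluded | Unvaccinated left | Power |
|---|---|---|
| 20 | 180 | about 79% |
| 40 | 160 | about 77% |
| 114 | 86 | about 68% |

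**The case against.** Several stronger readings are tempting, and the protocol does not support them.

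- **The window was derived from the 32.** A reader might infer this because 18 matches the lower limit and 31 sits just under 32. The protocol gives no reason for the limits, and a wide range suits the primary feasibility aim.
- **The 32 is the error and 26 is the correction.** Since 25 + 7 = 32 exactly, the catch-up range could be the mistaken figure. In that case the group above the programme ages would shrink or vanish.
- **Women of 28 to 31 were never offered the vaccine.** The protocol places them outside its stated programme ages but says nothing about vaccination outside the programme.
- **More than half the comparator is affected and power falls to 57%.** This needs uniform ages in two student populations and the adverse prevalence factor. The opposite factor raises power to 92%.

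Other objections also have weight. The 6% applies to women under 30, so it already includes ages 28 and 29; giving it to younger women only is a simplification. Against an 85% reduction the distortion of the ratio is small (0.14 to 0.17 instead of 0.15 in the 10% case). The coverage objective does not specify programme cohorts, so an all-participant denominator is not an error. Age adjustment is often left to an analysis plan, which is not shown here.

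These points limit the size of the finding and do not remove it. The contradiction is in the protocol itself, and so is the one comparison it specifies, by vaccination status alone. An analysis plan could add adjustment, but it would still need to know which birth cohorts the programme reached.

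**Conclusion.** The concern holds in a limited form. It is certain that the Background contradicts itself: its dates and catch-up ages give at most 26 in 2015 (27 in 2016), not 32. Conditional on 15 to 19 being right, and on little vaccination outside the programme, women of about 28 to 31 in 2016 belong almost wholly to the unvaccinated group, and the stated comparison ties vaccination to birth cohort.

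Neither the direction nor the size of the resulting bias can be derived from the protocol. Under the assumed 10% share and prevalence factors of 0.5 to 1.5, it is about ten per cent either way for a null vaccine, and up to about 7 percentage points of power are lost for the planned effect. That matters in a design with no margin above 80%, but it would not overturn an effect as large as the one planned. Severity is moderate, because the comparison is a secondary objective and the primary feasibility aim is untouched.

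**What to change.** 1. Reconcile the catch-up ages, the figure of 32 and the 18 to 31 window, and state which birth cohorts the programme targeted.
2. Make the vaccinated/unvaccinated comparison age-adjusted or stratified by birth cohort (school, catch-up, older than the programme), using the age already collected. Add a sensitivity analysis restricted to the targeted cohorts, because adjustment alone cannot supply vaccinated counterparts at ages that have almost none.
3. Report coverage both for all participants and for the targeted cohorts.
4. Keep all women in the feasibility and descriptive prevalence analyses.

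This needs a reconciled Background paragraph and a few sentences in the analysis section, with no new data. The cost is precision. In the restricted analysis, power is about 77% to 79% if 20 to 40 of 200 unvaccinated women drop out, but about 68% if 114 do. If the older women prove numerous, that loss is not slight, and the recruitment target for the comparison would need another look.
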